Despite these suggested therapeutic benefits of combined thermal ablation and embolization techniques, little is known about the prognostic effects of MWA + TAE in early-stage HCC. To our knowledge, no RCTs have compared the combination therapy (MWA + TAE) with monotherapy (MWA alone) in this selective cohort. The efficacy of MWA in combination with TAE as a prophylactic treatment to reduce recurrence in HCC patients with a small tumor burden is unknown. Moreover, the optimal protocol and timing for MWA combined with TAE as a treatment for early stage HCC has yet to be determined. For all of these reasons, RCTs are required to examine the feasibility as well as the possible therapeutic and/or survival benefits of combination MWA + TAE in selected patients with early-stage HCC.

STUDY DESIGN

Objective

This single-center, prospective RCT is designed to compare the outcomes and clinicopathologic results of blunt transarterial embolization (TAE) and microwave ablation (MWA) combination therapy with MWA monotherapy for the treatment of early (stages 0 and A) hepatocellular carcinoma (HCC). The primary aim of this study is to test the following hypothesis: 2-year intrahepatic disease-free survival does not differ between patients receiving the experimental therapy (MWA + TAE) and patients receiving the standard therapy (MWA alone) as treatment for early-stage HCC. Secondary aims are: 1) to determine the clinical feasibility of TAE + MWA in HCC patients with a small tumor burden using patient demographics and disease characteristic data and 2) to determine the effect of TAE on radiographic tumor characteristics in this patient cohort.

The primary outcome is 2-year intrahepatic disease-free survival, which is measured from time of randomization and is defined as the absence of local or regional recurrence of HCC as determined by diagnostic imaging. *Local recurrence* is defined as an enhancing lesion contiguous with the ablation zone that is present on subsequent imaging but was not present on the initial postablation scan. *Regional recurrence* is defined as hepatic recurrence that is not adjacent to the ablation site.

Secondary outcome measures include:

- Patient and disease characteristics (Table 1)
- 1-year, 2-year, 3-year, and 5-year overall survival;
- 1-year, 3-year, and 5-year intrahepatic disease-free survival;
- Number of TAE procedures required (for multilobar lesions or repeat effect)

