with either an open, laparoscopic, or robot-assisted laparoscopic approach. **The expected enrollment rate is 2 patients/month.**

Patients diagnosed with primary HCC classified as stage 0 (very early) or stage A (early) will be considered for inclusion in this study. Tumors will be staged preoperatively with computed tomography (CT) and/or magnetic resonance imaging (MRI). Laparoscopic ultrasound will be performed intraoperatively.

Eligible patients will meet the following inclusion criteria:

- Male or female patients aged ≥ 18 and ≤ 75 years
- Primary diagnosis of HCC according to the guidelines published by the American Association for the Study of Liver Diseases (AASLD)²⁸ and the diagnostic criteria used by the European Association for the Study of the Liver (EASL)²⁹:
 - Two imaging techniques showing typical features of HCC; or
 - Cytologic/histologic diagnosis of HCC; or
 - Radiographic classification as LIRAD 5 (Appendix III), regardless of AFP level.
- HCC classification of stage 0 (very early) or stage A (early) according to BCLC staging system criteria (Appendix I):
 - Solitary HCC lesion < 3 cm in diameter
 - ≤ 3 HCC lesions, each ≤ 3.0 cm in diameter
- Total bilirubin level, with or without portal hypertension, less than or equal to 3.0.
- Adequate clinical condition to undergo laparoscopic or robot-assisted laparoscopic TAE and/or MWA as treatment for HCC
- Willing and able to give informed consent

Patients meeting the inclusion criteria will be subjected also to the following exclusion criteria:

- Radiologic (CT or MRI) evidence of invasion into major portal/hepatic venous branches and no extrahepatic metastases (LR-5V or LR-M radiologic classifications)
- Evidence of residual disease at first post-MWA CT examination
- Body Mass Index (BMI) > 35
- Previous history of hepatic resections
- Severe renal dysfunction (creatinine clearance of < 40 mL/min)

- Pregnant or nursing women

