According to a computer-generated variable size blocked randomization method, eligible patients will be allocated on a 1:1 basis to receive the experimental therapy (MWA + TAE) and standard therapy (MWA alone), respectively. The nature of the treatments and their possible adverse effects preclude the use of double-blind and double dummy techniques. In patients randomized to receive the experimental therapy, TAE treatments will be initiated within one week of randomization, then followed by MWA within 4 to 6 weeks after reviewing radiological scans from TAE. MWA will be performed 4 to 6 weeks following randomization in MWA standard therapy groups. Treatment may be discontinued if any exclusion criteria develop in the patient or at the patient's request.

Sample Size

Power calculations are based upon expected 2-year survival rates. The main endpoint is 2-year intrahepatic disease-free survival, measured from the time of randomization which is measured from time of randomization and is defined as the absence of local or regional recurrence of HCC as determined by diagnostic imaging. Considering an estimated 80% and 90% intrahepatic disease-free survival at 2 years of follow-up for patients receiving MWA alone and MWA + TAE combination therapy, respectively, a sample size of 92 patients is required to detect a clinically meaningful 10% absolute difference in 2-year peritoneal disease-free survival with MWA + TAE with a minimum of 95% power and a 2-sided $\alpha = .05$. To account for a 5–10% withdrawal rate (following intraoperative detection of vascular invasion or extrahepatic metastasis, etc.), a sample size of 100 patients is required (50 patients per arm). If the rate of patient enrollment is suboptimal, a covariate adaptive randomization method will be used to allocate patients in a 2:1 ratio to receive experimental therapy (MWA + TAE) and standard therapy (MWA alone), respectively, which would result in an overall sample size of 83 patients.

Clinical Procedures

Preprocedural Strategy

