Incomplete ablation is defined as enhancement present at the ablation border on arterial phase CT consistent with residual tumor on the initial post-ablation scan. Local recurrence is defined as an enhancing lesion contiguous with the ablation zone that is present on subsequent imaging but was not present on the initial postablation scan. Regional recurrence is defined as hepatic recurrence that is not adjacent to the ablation site. Metastatic recurrence is defined as extra-hepatic recurrence including lymph node metastases. Expected residual disease is defined as disease that was intentionally left

untreated at the initial MWA session. Further, liver-directed therapy is defined as any secondary hepatic ablation procedure for incomplete ablation or any recurrent disease. Survival will be calculated from the time of randomization until last recorded follow-up, liver transplantation, or death.

Intrahepatic disease-free survival time is defined as the time between randomization and absence of local or regional recurrence of HCC as determined by diagnostic imaging. Overall survival will be measured as time from randomization until last recorded follow-up, liver transplantation, or death from any cause. Perioperative mortality is defined as in-hospital mortality.

Quality of Life

Quality of Life (QOL) will be assessed prospectively in a subgroup of patients who undergo follow-up examinations in the outpatient clinic of our facility. The data will be collected for a maximum of 5 years postoperatively or until patient death. Regular follow-up checkups will be offered to patients at 2-, 3-, or 6-month intervals depending upon time elapsed from surgery, with frequency of checkups decreasing as postoperative period increases in duration.

Statistical Analysis

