Patients alive at the time of analysis will be censored at the last follow-up examination or at liver transplantation. Univariate analyses will be performed using the log-rank test of equality for categorical variables and the chi-square test with Cox proportional hazard model for continuous variables to identify clinical variables (Child–Pugh class, Okuda class, Model for End-Stage Liver Disease (MELD) score, etiology of cirrhosis), tumor factors (extrahepatic disease, multicentric disease, tumor size, Milan criteria, AJCC tumor stage, AFP level), and treatment-related factors (TAE, complications, recurrence) predicting intrahepatic disease-free and overall survival. Survival and disease-free survival will be estimated using the Kaplan–Meier method and tested with the log-rank test following the intention-to-treat principle. Statistical analysis will be performed using SAS software (SAS Institute, Cary, NC, USA).

The analysis will be planned at a median follow-up of two years, with an interim analysis scheduled for 1 year after the first patient is enrolled or when 50% of total expected enrollment has been reached.

To improve patient selection in the future, additional exploratory analyses will be performed to identify potential prognostic factors. Table 1 details variables that will be included in a Cox proportional hazards regression model to obtain hazard ratios and 95% confidence intervals (CIs). All P values will be two-sided and a p value $< .05$ will be considered significant.

ETHICAL AND SAFETY CONSIDERATIONS

Protection of Patients

The techniques and procedures used in this study protocol are not investigational or provisional in nature; rather, they are established in the provision of care for patients of the HPB Division at Carolinas Medical Center. The therapeutic benefit of combination of TAE/MWA treatment in this patient population remains unknown and is the focus of this study. The additive risk for adverse events is expected to be equal to the individual risks of the study procedures in this protocol.

Standard Division-specific guidelines will be closely followed to ensure patient safety and clinical well-being during all procedures. Patients will be closely monitored for complications associated with MWA and TAE, including wound complications, hematologic toxicities, and others.

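### The protocol does not give one valid rule for liver transplantation in overall survival, and each way of reading it falls short of full intention-to-treat follow-up

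*Combined protocol and SAP*

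**What the plan says.** Three sentences govern the point.

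- Definitions (under Data Collection), for overall survival: "Overall survival will be measured as time from randomization until last recorded follow-up, liver transplantation, or death from any cause". A general sentence just before it sets the same end points: "Survival will be calculated from the time of randomization until last recorded follow-up, liver transplantation, or death". Neither is limited to patients alive at analysis, and neither says whether transplant counts as an event or as censoring.
- Statistical Analysis, first sentence: "Patients alive at the time of analysis will be censored at the last follow-up examination or at liver transplantation". This covers patients alive at the analysis. It gives no rule for a patient who is transplanted and later dies, and it is not limited to overall survival.
- The same paragraph says survival and disease-free survival are estimated by Kaplan-Meier and "tested with the log-rank test following the intention-to-treat principle".

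The secondary outcomes listed under Objective include "1-year, 2-year, 3-year, and 5-year overall survival". The protocol gives no expected transplant rate, no reason for stopping at transplant, no competing-risk method and no analysis that follows patients through transplant.

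**The concern.** Transplantation happens after randomization and may depend on tumour control and liver function. What is done with it therefore decides what the overall survival curve means. The two sections give an analyst at least three options: censor at transplant only those still alive, censor everyone at transplant, or count transplant as an event. They produce different estimates from the same data. Treatment is open, so a choice made after the data are seen could be made with arm-level results in view.

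The literal Statistical Analysis rule has a further defect. Whether a patient is censored at transplant depends on whether that patient later dies, whereas Kaplan-Meier requires that censoring carry no information about the later outcome.

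**Working it through.** The protocol states no figure that depends on the transplant rule, so there is nothing to reproduce. The check takes each reading in turn.

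**1. Literal Statistical Analysis rule**

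Transplanted survivors leave the risk set at transplant. Transplanted patients who die keep their full time and count as deaths. The deaths and their times are the same as with full follow-up, and the number at risk at each death is equal or smaller. Each Kaplan-Meier factor, 1 − deaths/at risk, is therefore equal or smaller, and so is the survival estimate.

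Hand example (all inputs assumed): 100 patients, 20 transplanted at month 12, 20% of these dying later, 20% deaths among the other 80, all deaths after month 12, no other censoring.

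- Deaths: 20 × 0.20 + 80 × 0.20 = 4 + 16 = 20.
- Full follow-up: 1 − 20/100 = 80.0%.
- Literal rule: the 16 transplanted survivors leave at month 12, so 84 remain at risk, and 1 − 20/84 = 76.2%. This is 3.8 points low.
- If 8 of the 16 non-transplant deaths fall before month 12: (1 − 8/100) × (1 − 12/76) = 0.920 × 0.842 = 77.5%. This is 2.5 points low.
- With 10% of the 20 dying later and all deaths after month 12: deaths 2 + 16 = 18, censored 18, and 1 − 18/82 = 78.0% against 82.0%. This is 4.0 points low.

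Simulation (assumed: 400,000 patients per scenario; exponential death and transplant times; 2-year survival 70–90%; 2-year transplant probability 10–30%; hazard of death after transplant 0.5 to 2 times that before; transplant unrelated to risk, or more frequent in sicker or fitter patients). Follow-up was either uniform over 0–50 months or at least 5 years for all. The 50 months come from 100 patients and "The expected enrollment rate is 2 patients/month", since 100/2 = 50. The resulting median of 25 months is close to the planned timing: "The analysis will be planned at a median follow-up of two years". The survival range is only scaled to the Sample Size section, which reads "Considering an estimated 80% and 90% intrahepatic disease-free survival at 2 years of follow-up"; those are disease-free rates, and no overall survival rate is given.

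The literal rule was low in every scenario: by 0.4 to 3.6 points at 2 years, and by 2.3 to 10.5 points at 5 years when all patients had at least 5 years of follow-up.

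**2. Everyone censored at transplant**

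Deaths after transplant are dropped and the direction of bias is not fixed. With 2-year survival of 80% before transplant, 20% transplanted by 2 years, transplant unrelated to risk and at least 5 years of follow-up, the transplant-censored estimate is 80.0% at 2 years and 57.2% at 5 years. Against it:

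| Hazard ratio after transplant | Full follow-up, 2 y | Full follow-up, 5 y | Bias at 5 y |
|---|---|---|---|
| 0.5 | 80.9% | 61.4% | 57.2 − 61.4 = −4.2 |
| 1 | 80.0% | 57.2% | 0 |
| 2 | 78.2% | 51.0% | 57.2 − 51.0 = +6.2 |

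If sicker patients are transplanted more often, the estimate is too high even at a hazard ratio of 1 (5-year 61.6% against 59.5%).

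**3. Transplant as an event**

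In the base case (hazard ratio 1) the 2-year figure becomes 64.0% against 80.0%. That is transplant-free survival, a different quantity.

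**4. Comparison between arms**

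- Identical arms: both curves fall together. In 20,000 simulated trials under the literal rule (50 per arm, 2-year survival 80%, 20% transplanted by 2 years, follow-up 0–50 months), the log-rank type I error was about 5%, the same as with full follow-up.
- Arms that differ, equal transplant use: repeat the hand example with 10% mortality in one arm. Deaths are 2 + 8 = 10, censored 18, and 1 − 10/82 = 87.8%. The difference becomes 87.8 − 76.2 = 11.6 points against a true 10.0. In simulation with 80% against 90%, it was about 10.7 against 10.0.

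**The case against.** A reader might infer that the plan contradicts intention-to-treat, lowers overall survival whatever happens, and distorts the arm comparison even when transplant use is equal. The documents do not support that much.

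- The two sections state alternative rules that cannot both operate. If Definitions governs and follow-up ends at transplant for everyone, later deaths are not counted and outcome-dependent censoring does not arise. It is reasonable to read Definitions as filling the gap in Statistical Analysis, because it gives the same end points twice. Downward bias is certain only under the literal Statistical Analysis reading. That censoring at transplant applies to survivors alone is an inference from silence.
- Patients are still analysed in their randomized arm. The conflict is with the complete follow-up that intention-to-treat implies, not with allocation.
- Equal transplant use does not by itself bias the comparison. With identical arms there is no bias; with a true 10-point difference the distortion was about 0.7 points in simulation and 1.6 in the hand example.
- Censoring at transplant can be a deliberate choice of a different quantity. The protocol does not say it is making that choice, and its definition names death from any cause.

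All of these limits stand. None supplies the missing rule for deaths after transplant, or says whether transplant is an event or censoring.

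**Conclusion.** The point holds as an unreconciled definition of a secondary outcome, and it should be corrected. No reading delivers overall survival with full intention-to-treat follow-up. The literal Statistical Analysis rule can only lower the estimate, by about 0.4 to 4 points at 2 years. Censoring everyone at transplant can err in either direction (from 4.2 points down to 6.2 points up at 5 years in the table). Counting transplant as an event changes the quantity. The arm comparison is biased when transplant use, mortality after transplant or underlying survival differs by arm.

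Only the direction under the literal rule follows from logic alone. Every size rests on assumed transplant rates, death rates and timing, because the protocol gives no transplant rate, no mortality after transplant and no overall survival rate. The upper end of the 2-year range further requires that no death precede transplant. A uniform downward bias, or a biased comparison between identical arms, is not established.

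**What to change.** In both Definitions and Statistical Analysis, define overall survival as time from randomization to death from any cause regardless of transplantation, censored only at the date last known alive. Report as a sensitivity analysis the version that censors all patients at transplant, whatever their later status. State separately how transplant is handled for intrahepatic disease-free survival, since the present censoring sentence is not limited to overall survival.

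The cost is revised wording and collection of vital status after transplant, within the horizon that 5-year survival already requires. A small downside is that the main overall survival estimate will then include the effect of transplant; the sensitivity analysis shows how much this matters.

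### The prognostic analyses use recurrence to predict the endpoint it defines, group overall survival by later recurrence, and put post-treatment items in a Cox model with far too few events

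*Combined protocol and SAP*

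**What the plan says.** The first paragraph of Statistical Analysis plans univariate analyses, with a log-rank test for categorical factors and a Cox-based test for continuous ones. The factors include "treatment-related factors (TAE, complications, recurrence) predicting intrahepatic disease-free and overall survival". The word recurrence is not qualified.

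Objective and Definitions both define intrahepatic DFS by the "absence of local or regional recurrence of HCC as determined by diagnostic imaging". Definitions also has a separate type outside that endpoint: "Metastatic recurrence is defined as extra-hepatic recurrence including lymph node metastases". OS is counted from randomization. No landmark, time-dependent covariate or restarted clock is described for recurrence.

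The last paragraph of the section says: "To improve patient selection in the future, additional exploratory analyses will be performed to identify potential prognostic factors". It continues: "Table 1 details variables that will be included in a Cox proportional hazards regression model". That sentence gives no endpoint, selection rule or limit on the number of variables. Table 1 mixes baseline items with intraoperative and postoperative ones. Its laboratory items carry no time point, although AFP is measured repeatedly.

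On timing: "The analysis will be planned at a median follow-up of two years". Under Patient Eligibility and Allocation: "The expected enrollment rate is 2 patients/month".

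**The concern.** There are three problems, all confined to the prognostic analyses.

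1. **Circularity.** If the predictor is the event that defines the outcome, every event falls in one group and the test says nothing.
2. **Immortal time.** A patient must stay alive long enough to recur. If the recurrence group is formed afterwards but followed from randomization, its months before recurrence are free of death by construction, while patients who die early without recurrence all count in the other group. The hazard ratio is pushed downward.
3. **Too many variables, some of the wrong kind.** The stated purpose is better patient selection. Items known only during or after treatment cannot serve it, and the expected events cannot support the listed number of variables.

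At stake is whether published prognostic statements, including whether recurrence shortens life, would be interpretable.

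**Working it through.** The plan gives no figure of its own for these analyses, so there is none to reproduce. The inputs are 100 patients at 2 per month, 1:1 allocation, and 2-year intrahepatic DFS of 80% (MWA) and 90% (MWA + TAE), all from the protocol. The documents give no OS for early-stage disease. I assume 5-year OS of 16%, 50% or 70%; the Background gives below 16% for HCC overall.

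**Time of the planned analysis.** The 50th of 100 patients enters at month 25 and reaches 24 months at month 49, when 98 are enrolled (49 per arm) with follow-up spread evenly over 0–49 months.

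**Intrahepatic DFS events at month 49.** Monthly recurrence rates are λ = −ln(0.8)/24 = 0.00930 and −ln(0.9)/24 = 0.00439. The monthly death rate is μ = −ln(5-year OS)/60. Per arm, expected events = 49 × λ/(λ+μ) × [1 − (1 − e^(−49(λ+μ)))/(49(λ+μ))].
- No deaths: 49 × 0.1968 + 49 × 0.1002 = 9.64 + 4.91 = 14.6.
- 5-year OS 70% (μ = 0.00594): 13.3.
- 5-year OS 50% (μ = 0.01155): 12.3.
- 5-year OS 16% (μ = 0.03054): 9.6, if that all-HCC figure applied here.

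**Part 1.** Follow the text: the predictor is local or regional recurrence yes/no, and the event is local or regional recurrence. The no-recurrence group has no events. Simulation is hardly needed, but it rejects in 100% of trials.

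**Part 2.** Simulated trials at month 49, 3000 runs per cell, with the death hazard multiplied by the stated hazard ratio (HR) after recurrence:

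| | 5-yr OS 16% | 50% | 70% |
|---|---|---|---|
| Expected deaths, no effect | 47 | 23 | 13 |
| True HR 1: median HR, ever-recurred groups | 0.46 | 0.45 | 0.44 |
| True HR 1: rejection | 23% | 11% | 3% |
| True HR 2: median HR, ever-recurred groups | 0.81 | 0.86 | 0.87 |
| True HR 1: median HR, time-dependent | 0.99 | 0.96 | 0.94 |
| True HR 1: rejection, time-dependent | 7% | 4% | 4% |
| True HR 2: median HR, time-dependent | 2.04 | 1.99 | 1.95 |
| True HR 2: power, time-dependent | 37% | 28% | 21% |

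Repeat runs of the grouped analysis with separate code gave median HRs of 0.44–0.49 (true 1) and 0.80–0.89 (true 2).

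**Part 3.** Table 1 count: patient 12–13, imaging 4, intraoperative 7–8, postoperative 6–10, tumor 5, laboratory 12, total 46–52. The range depends on how compound entries are split. From or after treatment: TAE and MWA applications, power and duration (4–5) plus postoperative (6–10) = 10–15. The number of TAE applications is zero in controls by design.

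Events per variable run from 12.3/52 = 0.24 to 14.6/46 = 0.32. I tested for an infinite estimate in one model with pure-noise covariates (200 runs, 14.6 events). At least one coefficient was infinite in 97.5–99% of trials with 46 variables and 99.5–100% with 52. With 34 variables it was still 70–77%; with 3–4 variables it was 0–10%. Deaths lower the event count, so they do not rescue the large model.

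**The case against.** **The sentence is a pooled list.** Recurrence may have been meant for OS only, where it is a sensible question, or only metastatic recurrence may have been meant. Either is possible, but the text names both endpoints and does not restrict the term. The reading without circularity has to be written in.

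**The analyst might use a time-dependent method anyway.** That the plan treats recurrence as known at randomization is inferred from what it does not say. Still, the test it prescribes, with OS counted from randomization, gives the biased comparison.

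**False positives.** A reader might infer that the OS test will mostly produce false findings. The documents do not support that for the planned analysis: null rejection is 3–11% at 5-year OS of 50–70%, and about 23% only at 16%, an all-HCC survival figure. It would rise to roughly 25–84% if the test were repeated at months 74–110. The Objective lists "1-year, 2-year, 3-year, and 5-year overall survival", but no repeat of the prognostic tests is scheduled. The main harm is the biased hazard ratio. Nor would a correct method reliably detect a doubled death rate at month 49.

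**One model is only one reading.** A candidate list or one-variable models may be intended, and the work is labelled exploratory. This objection stands in part: the infinite-estimate result is conditional on the one-model reading. The label does not make post-treatment items usable for selecting patients.

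**Later follow-up.** A reader might infer that the one-model problem fades with time. That holds only if deaths are ignored, so I rely on no later-horizon figures for the Table 1 model.

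**Conclusion.** The prognostic rules are wrong as written and should be changed. The circular DFS test follows from the text alone. The direction of the OS bias follows from the prescribed method. Its size rests on constant hazards, the plan's accrual and DFS rates, and assumed OS, but across 5-year OS of 16–70% the distortion barely moves: no effect appears as about 0.44–0.49, and a true HR of 2 as about 0.8–0.9. The mismatch in the Table 1 model, about 12–15 events against 46–52 items, uses the plan's rates with either no deaths or 5-year OS of 50–70%; heavier mortality makes it worse. The unnamed endpoint and model type are missing detail.

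A reader might go further and doubt the trial's main result. The documents do not support that: the arms are compared by Kaplan–Meier and log-rank under intention to treat, and none of these covariates enters that comparison.

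**What to change.** - Remove local and regional recurrence from the predictors of intrahepatic DFS. If metastatic recurrence is meant, say so.
- For OS, enter recurrence as a time-dependent covariate. A landmark analysis is an alternative at longer follow-up; a 12-month landmark has too few recurrences at month 49.
- Limit the Table 1 Cox model to treatment arm plus a few pre-named variables known before treatment, with baseline laboratory values. Leave out items arising from or after treatment. Portal-pedicle proximity and background liver pathology exist beforehand and may stay as candidates.
- State the model's endpoint, and whether it is one model or a set of one-variable models.

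Optional: a penalised or Firth-type Cox model, time-dependent handling of complications (the bias there is mild), and extending the exploratory label to the univariate paragraph.

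The cost is wording and a little programming, with no change to conduct or sample size. The downside is fewer reported factors and estimates that stay imprecise. Power for a recurrence HR of 2 on OS is about 21–37% at month 49. For a balanced binary baseline factor and DFS, SE = 1/√(0.25 × events) = 0.577 with 12 events and 0.516 with 15. The 95% interval is then the HR divided or multiplied by e^(1.96 SE) = 3.1 to 2.75, and 80% power needs an HR of e^(2.80 SE) = 5.0 to 4.25.

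### The interim analysis has two unreconciled triggers and no boundary; a .05 efficacy test at 50% enrolment would lift type I error to about 8–9.5%

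*Combined protocol and SAP*

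**What the plan says.** The timing of both analyses is set in one sentence of the Statistical Analysis section. Its first half fixes the final analysis: "The analysis will be planned at a median follow-up of two years". Its second half adds the interim: "with an interim analysis scheduled for 1 year after the first patient is enrolled or when 50% of total expected enrollment has been reached". The two conditions are joined by "or", with nothing to say whether the earlier, the later or either applies.

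The same section estimates survival and disease-free survival by the Kaplan–Meier "method and tested with the log-rank test following the intention-to-treat principle". Its closing paragraph, which otherwise deals with exploratory prognostic models, states "All P values will be two-sided" and sets significance at p < .05. The Sample Size section uses a two-sided alpha of .05 for the primary comparison and identifies it: "The main endpoint is 2-year intrahepatic disease-free survival, measured from the time of randomization".

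The calendar follows from two further statements. Patient Eligibility and Allocation says "The expected enrollment rate is 2 patients/month", and Sample Size says "a sample size of 100 patients is required (50 patients per arm"). No section gives an interim endpoint, a boundary, a division of alpha, a stopping rule or a monitoring committee.

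**The concern.** Two things are left open, and together they affect the error rate of the primary comparison.

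First, the two triggers are far apart at the planned accrual and yield very different amounts of data. Without a governing rule, the date of the look can be chosen after data have begun to accumulate.

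Second, a blanket .05 with no interim boundary means that any interim test of intrahepatic disease-free survival would be judged at the same level as the final one. Two chances to reject at .05 do not add up to a .05 trial. What is at stake is whether the stated two-sided .05 is true of the trial as a whole, and whether an early result based on a handful of events could be declared significant.

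**Working it through.** **Inputs.** Accrual 2 per month, 100 patients, 1:1, two-sided alpha .05, and 80% (MWA alone) and 90% (MWA + TAE) disease-free at 2 years, all from the protocol. Assumptions: even accrual; a constant hazard as the base case; as a sensitivity case, more of the 2-year hazard falling in year 1.

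**1. When the triggers fall.** One year after the first patient: month 12, with 2 × 12 = 24 enrolled. Half of 100: 50 / 2 = month 25, with 50 enrolled. Accrual ends at 100 / 2 = month 50. (Sample Size also allows a fallback total of 83, for which half is about 42 patients.)

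**2. Events available.** The monthly hazard is −ln(S)/24, so −ln(0.8)/24 = 0.00930 and −ln(0.9)/24 = 0.00439. With 1 patient per arm per month, expected events in an arm by month T (during accrual) are T − (1 − e^(−λT))/λ.
- T = 12: 0.65 + 0.31 = 0.96.
- T = 25: 2.69 + 1.32 = 4.0.

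Front-loaded hazards and a common 80% rate raise these, giving ranges of 1–2 events at month 12 and 4–7 at month 25.

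**3. Reference: the plan's own .05.** With one final test only, simulation under no treatment difference gives 4.9–5.2%. This reproduces the stated level.

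**4. Two looks at .05, normal approximation.** The correlation between looks is the square root of the information fraction. Expected events are about 15.1 at month 50 and 27.6 at month 74.
- Month 25 and month 50: fraction 4.0/15.1 = 0.27, correlation 0.52, chance that either look crosses 1.96 = 9.0%.
- Month 25 and month 74: fraction 4.0/27.6 = 0.15, result 9.4%.

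**5. Two looks at .05, simulated.** With so few events the approximation is rough, so the log-rank test was simulated. There were 40,000 null runs per setting, with a common 2-year rate of 85% or 80%, and 50% or 75% of the 2-year hazard in year 1. The test was run with and without truncation at 24 months, and the final analysis was placed at month 50, 57 or 74.

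| Rule | Overall type I error |
|---|---|
| Final only, .05 | 4.9–5.2% |
| Month 12 and final, both .05 | 5.1–6.3% |
| Month 25 and final, both .05 | 8.0–9.3% |
| Month 25 at .001, final at .05 | 4.9–5.2% |

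A second simulation (20,000 runs per rate, final at month 57) gave 5.1–5.2%, 8.1–8.6% and 4.7–5.0% for the last three rows. Taking steps 4 and 5 together, the month-25 figure is about 8–9.5%.

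**6. Why the two triggers differ.** With equal numbers at risk, each event contributes ±1/2 to the log-rank numerator and 1/4 to its variance. If all d events fall in one arm, |Z| = (d/2)/√(d/4) = √d.
- Crossing 1.96 needs d ≥ 1.96² = 3.84, so at least 4 events, all in one arm. With 1–2 events this can hardly happen, so the normal approximation's 9.6% for month 12 is too high and the simulated 5–6% is the figure to use.
- p < .001 needs |Z| > 3.29, so d ≥ 10.8, or 11 events all in one arm. With 7 events the maximum is √7 = 2.65. An interim at .001 therefore spends almost no alpha.

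**The case against.** The strongest reply is that the documents never say the interim tests the primary outcome. It may be meant as a safety or accrual check, and then no alpha is spent. That stands: a reader might infer that the trial's type I error is already inflated, and the text does not support so firm a statement. The inflation is conditional. What remains is that an analysis is scheduled with no purpose attached, and the only rule that could govern a test in it is .05.

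A second reply is that "or" may mean whichever comes first. At planned accrual that is month 12, where the inflation is at most about one percentage point. This also stands as arithmetic, but it means the look would rest on 24 patients and 1–2 events and would be of little use for any purpose that needs outcome data. A reader might conversely infer two interim looks; the sentence speaks of one.

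A third is that the .05 rule sits among the exploratory analyses. The Sample Size section states the same two-sided .05 for the primary comparison, so the intended level is not in doubt. It is not protected at the interim.

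A reader might also infer that a final analysis at a median of two years is a defect, because many patients would have less than 24 months of follow-up. The documents do not support that. The plan uses Kaplan–Meier and log-rank, and "Patients alive at the time of analysis will be censored at the last follow-up examination or at liver transplantation". If administrative censoring is unrelated to prognosis, these methods stay unbiased: simulated 2-year estimates average 0.800 and 0.900 whether the cutoff is month 48 or month 74. Precision is lower (standard error of the difference 0.083 at month 50 against 0.071 at month 74), but waiting would delay the read-out by roughly 18–25 months. That is a trade-off for the sponsor. Defining the median and the data cutoff would be a useful clarification and no more.

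**Conclusion.** The point holds for the interim analysis. Its trigger is ambiguous between month 12 and month 25, and it has no stated purpose or boundary. If intrahepatic disease-free survival is tested at .05 there and again at the end, overall two-sided type I error is about 8–9.5% for a look at 50% enrolment and about 5–6% for a look at 1 year. The stated .05 therefore fails at the 50% look and nearly holds at the 1-year look, which carries almost no information.

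These figures assume 100 patients allocated 1:1, even accrual at 2 per month and one interim. The range covers common 2-year rates of 80–85%, constant or front-loaded hazards, and a final analysis between months 50 and 74. The 83-patient 2:1 fallback was not simulated. The timing of the final analysis is not counted as an error.

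**What to change.** Keep one trigger, 50% of the enrolment target. State that the interim is a review of safety and feasibility, with no between-arm test of intrahepatic disease-free survival. The full .05 then belongs to the final analysis.

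If the sponsor does want an efficacy look, require p < .001 at the interim and keep .05 at the end. The overall level stays at about 5% (4.9–5.2% simulated).

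Either version changes a few sentences and adds no patients, visits or time. The one real cost is that stopping early for efficacy becomes practically impossible. With 4–7 events at that look, almost nothing is given up.
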